#### STEP 2: Creating the modified observed MDI rescue free dataset (Observed Dataset B)

The Observed Dataset A will be duplicated. Using the values in the duplicate dataset (Observed Dataset B) the Analysis Month where the MDI rescue sensor was permanently discontinued before the end of that month (and therefore presents a monthly rescue free rate based on partly observed sensor data for that month) will be imputed as missing; i.e. in Dataset B, if within an Analysis Month ( $D3 > 0$  and  $D3 < D5$ ) then set monthly value for that Analysis Month to missing. (Note: unless the participant is a completer in which case do not set the value to missing for that Analysis Month).

#### STEP 3: Creating the reference imputed datasets under MAR and J2R method

Using each of the two observed datasets (Observed Dataset A and Observed Dataset B) monthly values, create four separate reference imputed datasets (J2R-Dataset A, J2R-Dataset B, MAR-Dataset A, MAR-Dataset B) that account for the two imputation methods (J2R or MAR). Completely missing intermediate monthly values will be assumed MAR.

The multiple imputation will be implemented using the methods described in [Carpenter, 2013](#) using macros, Part1A, Part1B, Part2A and Part2B (available from <https://missingdata.lshtm.ac.uk/2017/04/06/gsk-five-macros/>). The seeds are documented at the end of Section [10.5.3.2](#) and 1000 draws will be used in the relevant macros parameters.

Due to the range of the rescue free days percentages being limited between 0 and 100, the multiple imputation process can generate percentages outside the possible range of values (< 0% or > 100%). A cap will be put in place where values imputed < 0 will be set as 0 and values imputed as > 100 set as 100.

#### STEP 4: Creating the Monthly Analysis values dataset

For each month within each participant create a count of each of the following durations based on intercurrent events: Let,  
 $r1$  = MDI rescue sensor still in use

**Percentage of Rescue Free Days Endpoint**

r2 = MDI rescue sensor discontinued but MDI rescue use ongoing until study withdrawal

r3 = MDI rescue discontinued at study withdrawal (includes days post withdrawal from the study). Note, if participant is a completer then for Analysis Month 6, r3=0.

r4 = r1 + r2 + r3

Note: it is assumed that MDI rescue use is not discontinued until permanent discontinuation of the study. Therefore, discontinuation date of MDI rescue use is the same date as permanent discontinuation of study

Set participants monthly values to observed, MARA, MARB, J2RA, J2RB imputation, no data each with a r1, r2, r3 duration.

Examples include to following:

- A participant who prematurely discontinues sensor after 20 days of Analysis Month 5 and withdraws from study after 5 days of Analysis Month 6

Subject Id	Draw	Month	A	B	J2RA	J2RB	MARA	MARB	r1	r2	r3	r4
X	1	1	77	77	77	77	77	77	28	0	0	28
X	1	2	82	82	82	82	82	82	28	0	0	28
X	1	3	87	87	87	87	87	87	28	0	0	28
X	1	4	77	77	77	77	77	77	28	0	0	28
X	1	5	71	.	71	77	71	78	20	8	0	28
X	1	6	.	.	80	79	77	76	0	5	23	28

- A participant who concurrently prematurely discontinues sensor and withdraws from study after 20 days of Analysis Month 5

Subject Id	Draw	Month	A	B	J2RA	J2RB	MARA	MARB	r1	r2	r3	r4
X	1	1	77	77	77	77	77	77	28	0	0	28
X	1	2	80	80	80	80	80	80	28	0	0	28
X	1	3	79	79	79	79	79	79	28	0	0	28
X	1	4	75	75	75	75	75	75	28	0	0	28
X	1	5	83	.	83	77	83	79	20	0	8	28
X	1	6	.	.	77	77	75	80	0	0	28	28

- A participant who completes the study after 27 days in Analysis Month 6

Subject Id	Draw	Month	A	B	J2RA	J2RB	MARA	MARB	r1	r2	r3	r4
X	1	1	77	77	77	77	77	77	28	0	0	28
X	1	2	82	82	82	82	82	82	28	0	0	28
X	1	3	87	87	87	87	87	87	28	0	0	28
X	1	4	77	77	77	77	77	77	28	0	0	28
X	1	5	80	80	80	80	80	80	28	0	0	28
X	1	6	82	82	82	82	82	82	15	12	0	27

For Arms 1 and 2,

- If the sensor is in use for at least a day within a month, r1>0 then let the analysis value be a combined value (weighted average) of the J2RA observed and MARB imputed values, by taking a proportion of each value based on the proportion of days the sensor is in use and not in use in that month

Percentage of Rescue Free Days Endpoint
--

Analysis value =  $r1/r4 \times (\text{value from J2RA}) + (r2+r3)/r4 \times (\text{value from MARB})$   
 Note the weight is, r4

- Else if the sensor was not used in the month,  $r1=0$  then let the analysis value be the imputed value,  
 Analysis value = value from J2RA dataset (which is the imputed value)

Implement special case of MAR post-early discontinuation of study by identifying participants where the MDI rescue sensor is prematurely discontinued and the participant concurrently withdraws from the study. Where study withdrawal has not been discontinued after the sensor but on the same day,  $r2=0$ .

- If the sensor is in use for at least a day within a month,  $r1>0$  then let the analysis value be a combined value (weighted average) of the J2RA observed and MARB imputed values, by taking a proportion of each value based on the proportion of days the MDI rescue was in use and not in use in that month

Analysis Value =  $r1/r4 \times (\text{value from J2RA}) + r3/r4 \times (\text{value from MARB})$

Note the weights are r4

- Else if the sensor was not used in the month,  $r1=0$  then let the analysis value be the imputed value,  
 Analysis value = value from MARA dataset (which is the imputed value)

For Arm 3 and 4,

- If the sensor is in use for at least a day within a month,  $r1>0$  then let the analysis value be a combined value (weighted average) of the J2RA observed and J2RB imputed values, by taking a proportion of each value based on the proportion of days the MDI sensor is in use and not in use in that month

Analysis value =  $r1/r4 \times (\text{value from J2RA}) + (r2+r3)/r4 \times (\text{value from J2RB})$

Note the weight is, r4

- Else if the sensor was not used in the month,  $r1=0$  then let the analysis value be the imputed value,  
 Analysis value = value from J2RA dataset (which is the imputed value)

Implement special case of MAR post-early discontinuation of study by identifying participants where the MDI rescue sensor is prematurely discontinued and the participant concurrently withdraws from the study and study withdrawal reason is not related to CIS. Where study withdrawal has not been discontinued after the sensor but on the same day,  $r2=0$ .

- If the sensor is in use for at least a day within a month,  $r1>0$  then let the analysis value be a combined value (weighted average) of the J2RA observed and MARB imputed values, by taking a proportion of each value based on the proportion of days the MDI rescue was in use and not in use in that month

Analysis Value =  $r1/r4 \times (\text{value from J2RA}) + r3/r4 \times (\text{value from MARB})$

Note the weights are r4

- Else if the sensor was not used in the month,  $r1=0$  then let the analysis value be the imputed value,  
 Analysis value = value from MARA dataset (which is the imputed value)

Implement special case of J2R post-early discontinuation of study by identifying participants where the MDI rescue sensor is prematurely discontinued and the participant concurrently withdraws from the study and study withdrawal reason is is related to CIS. Where study withdrawal has not been discontinued after the sensor but on the same day,  $r2=0$ .

Percentage of Rescue Free Days Endpoint

• If the sensor is in use for at least a day within a month, <math>r1>0</math> then let the analysis value be a combined value (weighted average) of the J2RA observed and J2RB imputed values, by taking a proportion of each value based on the proportion of days the MDI rescue was in use and not in use in that month Analysis Value = <math>r1/r4 \times (\text{value from J2RA}) + r3/r4 \times (\text{value from J2RB})</math> Note the weights are <math>r4</math>

• Else if the sensor was not used in the month, <math>r1=0</math> then let the analysis value be the imputed value, Analysis value = value from J2RA dataset (which is the imputed value)


STEP 5: Secondary Endpoint Percentage of Rescue Free Days Endpoint calculation
 
The calculations presented in the previous steps support the final derivation of the following secondary endpoint, the percentage of rescue free days between
 

○ the beginning of Month 4 and the end of Month 6

 
For participants who complete the study during the endpoint period of interest:
 
Analysis Endpoint is the average of monthly Analysis Values over the number of months in the endpoint period of interest, i.e.
 

○ Month 4 to Month 6

 
For participants who prematurely discontinue the study during the endpoint period of interest for reasons related or not related to CIS, the MAR or J2R imputation assumes participants would have continued in the study until the end of the period of interest. The weight is the total duration within the endpoint period of interest. This weight will be applied to each month within the period of interest and results summed together to produce the final endpoint/response variable for modelling within macro Part 3.
 
Note the weight is, total expected study duration within the period of interest. The proportion of weight to apply per monthly Analysis value is <math>r1+r2+r3/ \text{Total expected study duration within the period of interest}</math>.

Percentage of Rescue Free Days Endpoint
--

Seeds for Multiple Imputations Macros
--

Seeds for all planned MI analyses were determined in advance using the following SAS code and documented within this RAP prior to unblinding:

```

data temp;
  do i = 1 to 6;
    number=round(10000*ranuni(0),1);
    output;
  end;
run;
proc print;
run;

```

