**Table 4**

Intercurrent Event Estimation Rules (to be applied sequentially)	Intercurrent Event (IE)	Strategy with Rationale	Estimation Method following IE
1	
None (completed as randomised)
 
Without discontinuation of CIS feedback or MDI eSensor
 
 
Premature discontinuation from ELLIPTA eSensor
 
Premature discontinuation from ELLIPTA
 
Change of dose of ELLIPTA
 
 
Discontinuation of CIS feedback, but not MDI eSensor
 
 
Premature discontinuation from App and/or HCP interaction
 
	
Treatment policy:
 
Directly assessed using observed rescue data while MDI sensor is in use, regardless of whether the CIS feedback is discontinued.
	Data are available; no imputation required

Intercurrent Event Estimation Rules (to be applied sequentially)	Intercurrent Event (IE)	Strategy with Rationale	Estimation Method following IE
2	Discontinuation from MDI eSensor but not the study	Hypothetical:	MAR imputation (Arms 1&2) J2R imputation (Arms 3&4)
3	Premature withdrawal from the study	Hypothetical:	MAR imputation (Arms 1&2) J2R imputation (Arms 3&4)
4	Premature withdrawal from the study not related to CIS, and concurrent with discontinuation of the MDI sensor	Hypothetical:	Missing at Random (MAR) Imputation

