### 7.2.2.3.1. *Events following premature discontinuation of the MDI sensor*

It is assumed that participants would continue to take MDI as they would have without the CIS intervention (jump to reference imputation) following discontinuation of the MDI sensor if receiving treatment Arms 3 and 4, otherwise continue to take MDI as they would have with their allocated CIS interventions (MAR).

It is assumed that participants would continue to take MDI as they would have with their allocated CIS interventions (MAR) following concurrent discontinuation of MDI sensor and withdrawal from study if unrelated to CIS.

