### 7.2.2.5. **Statistical Analyses / Methodology Specification**

Endpoint / Variables
The percentage of rescue free days measured between the beginning of month 4 and the end of month 6 as determined by the MDI rescue sensor for the following treatment arm comparisons
Multiple Imputation Specification

Imputation will be carried out using monthly rescue free rates for months 1 to 6. 1000 draws will be used. For each draw, four intermediate imputation datasets will be created to allow for the handling of fully unobserved months (using set A imputations) and partially unobserved months (using set B imputations).
 
 
Set A where the partially observed month is directly estimated under the MAR assumption as the proportion of the number of days a participant is adherent divided by the number of days data provided in that month. 
 
J2R imputations
 
MAR imputations
 
 
 
Set B where the partially observed month is set to missing. 
 
J2R imputations
 
MAR imputations
 
 
 
 
The timing of the intercurrent events of discontinuation of the MDI sensor and withdrawal from study will be used to identify the proportion of each month to be assigned as observed data, J2R imputed data or MAR imputed data. The strategy for handling intercurrent events is described in Section 7.2.2.3 Strategy for Intercurrent (Post-Randomisation) Events.

Within each imputation draw, for each month, the observed and any imputed data will be combined to provide a percentage rescue free day value. The values for months 4 to 6 will be combined to create the value for the secondary analysis and the weight to be assigned to each participant.

Multiple imputation using Rubin's rules will be used to estimate the treatment effect and associated standard error, by performing the ANCOVA analysis described below on the secondary endpoint within each dataset.

The multiple imputation will be implemented using the methods described in Carpenter, 2013, using the macros available from <https://missingdata.lshtm.ac.uk/2017/04/06/qsk-five-macros/>.

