### Model Results Presentation

Summary statistics (mean, standard deviation, median, minimum, maximum) of the primary endpoint will be provided, based on the observed percentages.

The adjusted means for each treatment and the estimated treatment difference for the treatment comparisons of Arm 1 versus Arm 5, Arm 2 versus Arm 5, Arm 3 versus Arm 5 and Arm 4 versus Arm 5 will be presented together with the 95% confidence interval for the differences and corresponding p-values from

the multiple imputation procedure.

Endpoint / Variables
Total rescue use measured between the beginning of month 4 and the end of month 6 as determined by the MDI rescue sensor
Summary

The endpoint will be summarised using descriptive statistics (n, mean, SD, median, min, max) for each treatment arm.
 
To explore the effect of 6 months use of the CIS on a participant's rescue medicine usage, the following displays will be presented,
 
 
Summary statistics (n, mean, SD, median, min, max) of Total rescue use measured between the beginning of month 4 and the end of month 6 as determined by the MDI rescue sensor
 
Total rescue use will be summarized by each individual month (Month 1 – Month 6) and then displayed as a total between month 4 – 6.
 

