### Intercurrent Event Patterns

### Intercurrent Event 'Estimation Rules' 1-4

a. J2R imputation if withdrawal related to CIS; MAR imputation if withdrawal not related to CIS

Percentage of Rescue Free Days Endpoint
Intercurrent Events related to CIS
In order to implement the intercurrent event strategy detailed in Section 7.2.2.3 Strategy for Intercurrent (Post-Randomisation) Events, it is necessary to determine if and when the reasons for permanent discontinuations related to CIS occur.
The date and reason for withdrawing from the study will be determined from the study conclusion page of the eCRF.
Study discontinuation reasons classified as related to CIS are as follows:

 
Withdrew consent – dissatisfaction with the connected inhaler system (CIS)
 

Percentage of Rescue Free Days Endpoint
Monthly Percentage of Rescue Free Days - Calculation
STEP 1: Creating the observed adherence dataset (Observed Dataset A)
To determine the monthly observed percentage of rescue free days values (Observed Dataset A) the following should be applied for each month:
For Baseline Analysis Month, for each participant create a count of each of the following types of Days
D1 = Rescue use recorded
D2 = Device incident
D3 = Post discontinuation of MDI rescue sensor
D4 = MDI rescue free
D5=D1 + D2 + D3 + D4, i.e. The total number of days within the Baseline Analysis Month; the total number of days between Beginning Timepoint and Ending Timepoint as defined in Table 5 in Section 10.2 Appendix 2: Assessment Windows .
For Analysis Month 1, 2, 3, 4 and 5, for each participant create a count of each of the following types of days:
D1 = Rescue use recorded
D2 = Device incident
D3 = Post discontinuation of MDI rescue sensor
D4 = MDI rescue free
D5 = D1 + D2 + D3 + D4, i.e. The total number of days within the Analysis Month; the total number of days between Beginning Timepoint and Ending Timepoint as defined in Table 5 in Section 10.2 Appendix 2: Assessment Windows .
For Analysis Month 6, for each participant create a count of each of the following types of days:
D1 = Rescue use recorded
D2 = Device incident
D3 = Post discontinuation of MDI rescue sensor
D4 = MDI rescue free

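### Rescue-free days: for Arms 1 and 2, months with no MDI sensor use after a non-concurrent sensor stop are filled by jump to reference, although the SAP declares missing at random for those arms

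*SAP*

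**What the plan says.** Table 4 in SAP 7.2.2.3 sets the strategy for rescue-free days. For a participant who stops the MDI sensor but stays in the study (rule 2), and for premature withdrawal (rule 3), it gives "MAR imputation (Arms 1&2) J2R imputation (Arms 3&4". Section 7.2.2.3.1 repeats this: participants in Arms 3 and 4 jump to reference, and the others "otherwise continue to take MDI as they would have with their allocated CIS interventions (MAR".

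The multiple-imputation specification in 7.2.2.5 creates four imputed datasets to allow for "handling of fully unobserved months (using set A imputations) and partially unobserved months (using set B imputations". A wholly unobserved month therefore draws on set A: J2RA or MARA, according to the strategy.

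Step 4 of SAP 10.5.3.2 turns this into programming rules. Here r1 is the number of days in the month with the sensor in use, r2 the days after the sensor stop but before withdrawal, r3 the days after withdrawal, and r4 their sum. Under the block for Arms 1 and 2:

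- r1 > 0: the observed value (held in J2RA) is weighted by r1/r4 and the MARB value by (r2+r3)/r4.
- r1 = 0: "Analysis value = value from J2RA dataset (which is the imputed value".
- Special case, sensor stop and withdrawal concurrent, r1 = 0: "Analysis value = value from MARA dataset (which is the imputed value".

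**The concern.** Three of the four places that govern Arms 1 and 2 after a sensor stop apply MAR: the strategy text, the partly observed month, and the concurrent-withdrawal case. The fourth, the general r1 = 0 line, applies J2R. One participant can then be imputed under MAR for the rest of the month in which the sensor stopped and under J2R for every later month. Two participants in the same arm get different assumptions only because one stopped the sensor on the day of withdrawal and the other did not.

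The declared choice fits the design. Arms 1 and 2 receive no rescue-sensor data (Protocol Table 1), so stopping that sensor removes no feedback, and the SAP gives no reason to treat such a participant as an Arm 5 participant. At stake are the Arm 1 versus Arm 5 and Arm 2 versus Arm 5 estimates on a listed secondary endpoint. SAP 7.2.2.5 reports these with confidence intervals and p-values: "The adjusted means for each treatment and the estimated treatment difference for the treatment comparisons of Arm 1 versus Arm 5" and the corresponding comparisons for the other arms.

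**Working it through.** **Which value the r1 = 0 line delivers.** When r1 > 0, the J2RA column holds the directly observed monthly rate, so its use there is harmless. When r1 = 0 nothing was observed, and J2RA is a jump-to-reference draw. The first worked example in Step 4 shows the two columns differing in such a month: J2RA 80, MARA 77.

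**Whether another passage reconciles the conflict.**

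- Step 3 states: "Completely missing intermediate monthly values will be assumed MAR". Months after a permanent stop are not intermediate, so this does not reach them.
- With r2 = 0, the partial-month formula of the concurrent special case equals the general one. The special case changes only the r1 = 0 line, from J2RA to MARA, and only for concurrent stops.
- SAP Table 1, which lists changes from the protocol analysis, has no entry that explains the rule.
- The adherence derivation (SAP 10.5.3.1, Step 4) contains the same J2RA sentence. There J2R is the declared strategy, so the sentence may have been carried over.

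**Worked example, read as an Arm 1 or 2 participant.** The sensor stops after 20 days of Month 5 and the participant withdraws after 5 days of Month 6.

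- Month 4 = 77.
- Month 5 = 20/28 × 71 + 8/28 × 78 = 73.00.
- Month 6 (r1 = 0) = 80 as written, or 77 under MAR.
- Each month carries weight 28/84 = 1/3 (Step 5).
- Months 4 to 6 as written: (77 + 73 + 80)/3 = 76.67. Under MAR: (77 + 73 + 77)/3 = 75.67.

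The SAP states no final value for this example, so there is no published figure to reproduce. The 1.00-point gap comes from one illustrative draw, and the two datasets use different seeds (8350 for J2RA, 2553 for MARA). It is not an estimate of bias.

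**Expected size.** Assume a common covariance across arms and a constant monthly difference D between the arm and Arm 5. Both imputations then share the same regression on the participant's earlier months, so the expected J2R minus MAR gap in a month is the Arm 5 mean minus the own-arm mean, that is −D. With k of the three months wholly unobserved, the participant's endpoint shifts by −D × k/3. If a share p of the arm is affected, the arm difference shrinks by the fraction p × k/3. The documents do not give p, so the values below are assumptions:

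| p | k = 1 | k = 2 | k = 3 |
|---|---|---|---|
| 2% | 0.67% | 1.33% | 2.00% |
| 5% | 1.67% | 3.33% | 5.00% |
| 10% | 3.33% | 6.67% | 10.00% |

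For an assumed D of 10 points this is 0.07 (p = 2%, k = 1) to 1.0 points (p = 10%, k = 3).

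**Simulation check of the shift per participant.** Assumed: six monthly values, SD 25, within-person correlation 0.3 to 0.8, Arm 5 mean 50, known parameters, independent draws for the two methods, 100,000 participants per setting. For D = 10 the mean shift was −3.3, −6.6 to −6.8 and −10.0 points for k = 1, 2 and 3. The formula gives −3.3, −6.7 and −10.0. The SAP's cap at 0 and 100 made the shift about 5% to 6% smaller. The SD of a single participant's one-draw gap was 6 to 21 points, so the gap in the worked example lies well within draw noise.

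**The case against.** The conflict in the text is hard to dispute; the serious objections concern its weight.

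- *The worked example proves little.* Its monthly percentages are identical to those in the first adherence example, only the day counts differ, and it names no arm. Read as Arm 3 or 4, J2RA is the declared value. This stands: the example shows only that the two columns can differ.
- *The size rests on assumptions.* Nothing in the documents supports a 10% share of non-concurrent stops or a 10-point difference, and the amendment rationale reports dropout well below expectation. This also stands, although dropout does not measure sensor stops.
- *The effect is small against the noise.* With 76 per arm, SD 25 and correlation 0.3 to 0.8, the three-month mean has SD 25 × √((1 + 2ρ)/3) = 18.3 to 23.3. The unadjusted 95% half-width is then 1.96 × SD × √(2/76) = 5.8 to 7.4 points. A shift of 1.0 is at most about 17% of that. This bears on urgency; it does not make the line correct.
- *The schematic cannot be judged.* Its surviving footnote reads "J2R imputation if withdrawal related to CIS; MAR imputation if withdrawal not related to CIS" and names no arms, while Step 4 applies MAR to concurrent withdrawals in Arms 1 and 2 whatever the reason. The drawing is not available, so this supports a check and nothing more.

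**Conclusion.** The concern holds. The r1 = 0 line for Arms 1 and 2 contradicts Table 4 and section 7.2.2.3.1, and no other passage resolves the contradiction. A programmer who follows Step 4 and one who follows Table 4 would produce different estimates. In expectation the line as written pulls Arms 1 and 2 towards Arm 5 wherever the arms differ; for a single participant the shift can go either way. Its true size is unknown because the documents do not say how many participants stop the MDI sensor without withdrawing on the same day. The attenuation range in the table depends on the assumed share, the number of months lost, a constant monthly difference and a common covariance. Reach is limited to a secondary endpoint whose comparisons SAP 2.4 declares descriptive. It should be corrected, but it does not threaten the trial's main conclusion.

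**What to change.** Before unblinding, in SAP 10.5.3.2, Step 4, block for Arms 1 and 2, change J2RA to MARA in the line for a month with r1 = 0. Then check that the intercurrent-event schematic and its footnote agree with Table 4 and section 7.2.2.3.1 for those arms. If jump to reference was in fact intended there, Table 4 and 7.2.2.3.1 must be changed instead, with a rationale for arms that receive no rescue data. The cost is one word and one check; no new data or additional analysis is needed.
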